13.2.4 Interim analysis

For this study no formal interim analysis is planned.

13.2.5 Software documentation

The statistical analysis will be performed with the Stata software. We will use the Stata 17 version or the last most up to date available version when analysis takes place. Scripts used in the analysis can be published as supplementary material of the main publication or uploaded into a public repository

This project is part of the EDCTP2 programme supported by the European Union

14. Data management

14.1 Type of data that will be collected

a) Participants' personal data

This trial will collect pseudonymized demographic and clinical data. This includes variables such as TB symptoms, weight, height, medical history (history of diabetes, renal failure, others), current and past medication, HIV status, ART use, tobacco and alcohol use, previous TB episodes, existence of TB contact at home, among others.

b) Laboratory parameters (biological data) derived from laboratory analyses of participants' specimens

Results from all TB microbiological assays performed to patients including CD4 counts (if not available within the last 3 months) and HIV test (if not documented status available), will be linked to study participant's information through a unique study identifier number. All samples and databases will not contain patient's name but only laboratory barcodes and anonymized patient study numbers.

14.2 CRFs

We have developed 10 main CRFs for all participants:

- Consent & Eligibility CRF
- Baseline Characteristics CRF
- Specimen Collection CRF
- AlereLAM & CRP CRF
- FujiLAM Results CRF
- Xpert Ultra Tongue Swab Results CRF
- Lumira Dx Test Results CRF
- Hospitalization assessment CRF
- 4 Week visit CRF
- 8 Week visit CRF
- Lab results CRF (including TB specific and other lab results (CD4 counts, viral load)
- Study Completion CRF (whenever a patient stops being part of the study (completed all procedures -at week 8), death before week 8, or LTFU at any point within the first 8 weeks).

This project is part of the EDCTP2 programme supported by the European Union

In addition, a retrospective local standard of care CRF will be used (Retrospective CRF).

The Lab result CRF might be used at any point within the study period if additional TB tests are performed on the patient.

14.3 Data entry

Data will be collected on paper based CRFs and entered to a secured encrypted and password protected electronic CRF system using OpenClinica® Software (Enterprise version 4), a secure web application for building and managing online surveys and databases. While OpenClinica can be used to collect virtually any type of data, it is specifically geared to support online data capture for research studies and operations.

Data collection and entry will be performed by study specific personnel trained in data collection and human subjects data protection. Data managers will design the electronic CRF, ensure all data quality and provide support whenever a problem occurs. Each completed CRF should be data entered within a week from its completion.

Although main data capture will be based on paper CRFs replicating electronic CRFs, there will be handwritten data source documentation (additional patient medical history, HIV proofs, X ray data, printouts of Ultra results, clinical follow up information and other), which will be kept with patient study files locally and that might be used for data quality checks. All personnel with direct access to data will be trained on human subjects' data protection and maintain training records.

Different data access privileges to OpenClinica will be set for different user types (local data clerks, local data managers, local study coordinators, site PIs, and project overall data manager from LMU). The Site PI and site project manager/study coordinator are responsible for assuring that the data entered into OpenClinica is complete, accurate, and recorded in a timely manner.

In addition to data capture, sites will maintain logbooks to record the dates of completed and upcoming study visits, specimen collection, transport and receipt at the respective laboratories, and time of receipt of test results. Laboratory tests will be requested on study laboratory test requisition forms. All logbooks and laboratory requisition forms will be kept in locked filing cabinets when not in use and will be accessible only by designated clinic personnel.

14.4 Data monitoring and quality assurance

Electronic CRFs will be designed in order to minimize data capture errors. Drop-down menus, data range limits/edit checks and data type protection will be included in open data collection fields. Data will be curated by local data clerks and routine data checks performed by local data managers. The project main data manager at LMU will periodically generate a list of data queries

This project is part of the EDCTP2 programme supported by the European Union

derived from the reconciliation of different clinical and lab project data. Automated syntaxes will be designed in order to improve the efficiency of the quality assurance process.

No official onsite data monitoring visits will be done in this study. Central/remote monitoring will happen remotely through LMU/FIND.

14.5 Record retention

Study records (source documents, signed informed consent forms, IRB/IEC correspondence and approval letters, and screening logs) will be kept in a secure location accessible only to authorized study staff, investigators, and monitors. Secure archives are available at the sites for preliminary storage after study closure, before moving them to an off-site, secure storage facility. All records will be archived in a secure storage facility for at least ten years after the completion of the study.

This project is part of the EDCTP2 programme supported by the European Union

15. Ethical considerations

This study will be conducted according to the ethical principles set forth in the Declaration of Helsinki, ICH-GCP, and local regulatory requirements as applicable.

Written informed consent will be obtained from each participant prior to any protocol-specified procedures being conducted. An added IC for specimen storage (and future use) might be required at some sites. The protocol and informed consent form(s) will be reviewed and approved by the IRB or IEC of each participating clinical site prior to patient enrollment. Site investigators are responsible for ensuring that the protocol is reviewed by an IRB/IEC with the appropriate composition (per site guidelines). The investigator will inform the IRB/IEC as to the progress of the study at applicable intervals as defined by IRB/IEC policy. Depending on national policies, the protocol might be reviewed by national regulatory authorities.

FIND will act as the main sponsor for this study. Delegated responsibilities will be assigned locally and documented. FIND holds Public Liability ("negligent harm") and Clinical Trial ("non-negligent harm") insurance policies which apply to this trial.

15.1 Confidentiality

Adequate measures to ensure personal data protection and confidentiality will be taken, according to the European General Data Protection Regulation (EU) 2016/679 (GDPR) on the protection of natural persons with regard to the processing of personal data and on the free movement of such data. National regulations on personal data protection will be implemented to safeguard patients' confidentiality throughout the duration of the clinical trial.

All study related data (study CRFs and clinical specimens) will be pseudonymized linked to an individual patient study number, and samples will be numbered/barcoded in accordance. Names or other obvious identifiers will not be used on study CRFs, they only will appear at each site on source documents. Any hardcopy links between patient names and patient study numbers or data will be kept in a locked cabinet at each study site, under the responsibility of the PI/site coordinator. All informed consent forms will also be maintained in a locked cabinet at each of the sites. All study personnel and investigators will be trained prior to study initiation on all aspects related to patient's confidentiality. Study results will be reported and published in summary form without any patient-identifying information.

16. Timeline

| | 2021 | | | 2022 | | | | | | | | | | | | 2023 | | | | | 2024 | | | | | |
|---------------------------|------|---|---|------|---|---|---|---|---|---|---|---|---|---|---|------|---|---|---|---|------|---|---|---|---|--|
| | S | O | N | D | J | F | M | A | M | J | J | A | S | O | N | D | J | F | M | A | M | J | J | A | S | |
| Final protocol amendment | | | | | | | | | | | | | | | | | | | | | | | | | | |
| Ethics clearance | | | | | | | | | | | | | | | | | | | | | | | | | | |
| SOP writing (review) | | | | | | | | | | | | | | | | | | | | | | | | | | |
| CRFs eCRF Design (review) | | | | | | | | | | | | | | | | | | | | | | | | | | |
| Training/Study Initiation | | | | | | | | | | | | | | | | | | | | | | | | | | |
| Dry run | | | | | | | | | | | | | | | | | | | | | | | | | | |
| Recruitment period | | | | | | | | | | | | | | | | | | | | | | | | | | |
| Follow up period | | | | | | | | | | | | | | | | | | | | | | | | | | |
| Data Cleaning | | | | | | | | | | | | | | | | | | | | | | | | | | |
| Analysis/Report writing | | | | | | | | | | | | | | | | | | | | | | | | | | |
| Capacity building SG | | | | | | | | | | | | | | | | | | | | | | | | | | |

Appendix 1: Incident Definition and Reporting

Incident: Any malfunction or deterioration in the characteristics and/or performance of a device, as well as any inadequacy in the labeling or the instructions for use which, directly or indirectly, might lead to or might have led to the death of a patient, or USER or of other persons or to a serious deterioration in their state of health.

The following criteria as defined in sections 1.1, 1.2 and 1.3 are to be considered to determine whether an adverse incident has occurred. Please note that all three criteria must be met to be deemed as reportable. Please also refer to MEDDEV 2.12-1, Guidelines on a Medical Devices Vigilance System for further guidance.

1.1 *An Event has Occurred*

This also includes situations where testing performed on the device, examination of the information supplied with the device or any scientific information indicates some factor that could lead or has led to an event.

Typical events include, but are not limited to:

- 1.1.1 A malfunction or deterioration in the characteristics or performance (should be for intended purpose and follow manufacturer's instructions).
- 1.1.2 For IVDs where there is a risk that an erroneous result would either (1) lead to a patient management decision resulting in an imminent life-threatening situation to the individual being tested, or to the individual's offspring, or (2) cause death or severe disability to the individual or foetus being tested, or to the individual's offspring, all false positive or false negative test results shall be considered as events.
- For all other IVDs, false positive or false negative test result falling outside the declared performance of the test shall be considered as events.
- 1.1.3 Unanticipated adverse reaction or side effect.
- 1.1.4 Interactions with other substances or products.
- 1.1.5 Degradation / destruction of the device.
- 1.1.6 Inappropriate therapy.
- 1.1.7 Inaccurate labelling, Instructions for Use (IFU) and / or promotional materials (includes omissions and deficiencies but not those generally known by user).

1.2 *The Manufacturer's Device is Suspected to be a Contributory Cause of the Incident*

- 1.2.1 In assessing the link between the device and the Incident, the Manufacturer should take account of:
 - 1.2.1.1 Results of the manufacturer's own preliminary assessment of the incident.
 - 1.2.1.2 Evidence of previous, similar incidents.
 - 1.2.1.3 Any other relevant evidence held by the manufacturer.
- 1.2.2 Where there are a number of devices involved, the manufacturer should always assume their device contributed to the incident until proven otherwise.

1.3 *The Event Led, or Might Have Led, to One of the Following:*

- 1.3.1 The death of a patient, user or other person.
- 1.3.2 Serious deterioration in the health of a patient, user or other person that can include:
- 1.3.3 Life-threatening illness.
- 1.3.4 Permanent impairment of a body function or permanent damage to a body structure.
- 1.3.5 A condition necessitating medical or surgical intervention to prevent the two points above; for example clinically relevant increase in surgical procedure, a condition requiring hospitalisation or prolongation of existing hospitalisation.
- 1.3.6 Any indirect harm as a consequence of incorrect diagnostic or IVD test result when used within the manufacturer's IFU (use errors reportable under section 5.1.5.1 of MEDDEV 2.12/1 must also be considered)
- 1.3.7 Foetal distress, foetal death or any congenital abnormality or birth defect.

Appendix 2: FujiLAM testing

[figure not shown]

Figure 1: FujiLAM TB test device, test procedure and test principle. (MTX-Man refers to mannose caps further modified with a 5-methylthio-D-xylofuranose residue). Au=gold. C=control line. MTX-LAM=5-methylthio-D-xylofuranose-lipoarabinomannan. T=test line. Image obtained from Broger et al, 2019.³¹

---

## 1 Abbreviations and Definitions

AE	Adverse Event
AlereLAM	Alere Determine TB LAM Ag
CRF	Case Report Form
DMP	Data Management Plan
FujiLAM	Fujifilm SILVAMP TB LAM
HIV	Human immunodeficiency virus
IMP	Investigational Medical Product
ITT	Intention to treat
KPS*	Karnofsky Performance Status Scale definitions rating (%) criteria
LF-LAM	Lateral flow urine lipoarabinomannan assay
PP	Per Protocol
SAP	Statistical Analysis Plan
TB	Tuberculosis
Ultra	Xpert MTB/RIF Ultra

## 2 Introduction

### 2.1 Preface

Tuberculosis (TB) is a leading cause of death worldwide and ranks above HIV/AIDS as the leading cause of mortality from a single infectious agent. The World Health Organization (WHO) estimated that there were around 10 million new cases and 1.5 million deaths in 2021. Eight and 14% of the total number of TB cases and deaths respectively occurred in people living with HIV (PLHIV), with 70% of these occurring in the African region. PLHIV are at increased risk of acquiring *Mycobacterium tuberculosis* (Mtb) infection and have a >20-fold increased risk of TB disease progression compared to HIV-uninfected peers. In addition, mortality during TB treatment remains as high as 11% globally, although fatal outcomes of PLHIV under TB treatment are even higher in Sub-Saharan African countries

Among people living with HIV, microbiological confirmation of TB is suboptimal due to sputum collection challenges and paucibacillary sputum resulting in poor diagnostic yield. Options that have been recommended by WHO to ensure earlier diagnosis and reduce mortality include strategic placement of rapid molecular TB diagnostics such as Xpert or Ultra within HIV care settings (which could enable availability of results within 24 hours), and uptake of the urine lipoarabinomannan assay (LF-LAM) strip-test, the Alere Determine™ TB LAM Ag (AlereLAM), for seriously ill or immunosuppressed PLHIV. However, despite AlereLAM being a cheap and fast test, only 9 of the 30 high TB and HIV burden countries had in 2020 a national policy and algorithm indicating the routine use of urine LF-LAM (with various levels of implementation). In addition, PLHIV often are sputum paucibacillary and a considerable proportion of them cannot provide a good quality sputum specimen for molecular testing.

The limitations of existing sputum-based tests for *M. tuberculosis* (Mtb) diagnosis among (PLHIV) admitted to hospital create imperatives to explore the usefulness of easy to collect, non-respiratory specimens which could improve TB diagnosis, while supporting and accelerating treatment guidance. Previous studies have shown that Xpert testing of urine and stool can confirm Mtb in participants who would otherwise test negative with traditional sputum-based methods. Evidence shows that these diagnostics may detect additional cases that are not detected by AlereLAM. Thus, an algorithm using the different tests (sputum Ultra, urine Ultra and stool Ultra) offered as a screening intervention to admitted HIV positive participants should increase the Mtb bacteriological yield (compared to current WHO recommended screening and testing strategies\*\*) and contribute to earlier initiation of TB treatment. Given that some detected cases may not present with classical TB symptoms at the time of hospitalization, we believe that this strategy will increase the overall number of participants with diagnosed TB and started on treatment and ultimately reducing mortality.

### 3 Study Objectives and Endpoints

#### 3.1 Main Study Objectives

The primary objective of the study is to investigate the effect of an expanded TB screening strategy performed in HIV-positive participants admitted to hospital on the proportion of bacteriologically confirmed TB cases starting treatment within 72 hours of enrolment

**INTERVENTION ARM** (expanded TB screening strategy): Xpert Ultra on sputum, stool/rectal swab and AlereLAM on urine, performed regardless of presence of TB symptoms

**CONTROL ARM:** Ultra testing (on sputum/any tissue) if TB-compatible symptoms and AlereLAM (on urine) only in those fulfilling WHO testing recommendations.

#### 3.2 Secondary and Exploratory Study Objectives

The study has the following secondary objectives.

##### Secondary objectives

1. To assess the impact of this screening strategy on 2-month all-cause mortality.
2. To assess the feasibility of multiple specimen collection for TB diagnosis within 72 hours of enrolment.

*\*to the main protocol includes additional exploratory objectives, which will be specified in a separate SAP*

#### 3.3 Study design

This is a multicentre, parallel, individually randomized, controlled diagnostic trial in consecutively enrolled HIV positive adults admitted to hospital in selected sites in Mozambique and Tanzania.

This trial has two study arms, the intervention and control arm. The intervention arm for this study consists of HIV participants with TB testing performed regardless of presence of TB symptoms. Testing will be done on expectorated sputum, stool/rectal swab and concentrated urine with Ultra and urine with AlereLAM.

The **control arm** for this trial will consist of participants managed according to the current WHO recommended TB testing practices for HIV positive participants (as of Q1 2022). TB testing will be done as follows:

**Sputum Ultra** performed whenever the patient has cough, fever, weight loss overnight sweats and/or

**Ultra performed on any tissue** (including lymph nodes) from participants with clinical suspicion of extrapulmonary TB.

and/or:

**Urine Alere TB-LAM** performed if participants have signs and symptoms of TB (pulmonary and/or extrapulmonary), or with advanced HIV disease, or who are seriously ill, or else irrespective of signs and symptoms of TB, but combined with a CD4 cell count of less than 200 cells/mm^3.

### 3.4 Endpoints

All study endpoints will be compared between control and intervention arm. Also, the final results will be presented disaggregated by sex.

3.4.1 The **primary endpoint** is the proportion of participants diagnosed with microbiologically confirmed TB and started on TB treatment within 72 hours of enrolment\* in whom TB is microbiologically confirmed\*/\*\*

\* The numerator of the primary endpoint includes participants per study arm who are diagnosed with microbiologically confirmed TB and initiated TB treatment within 72 hrs of enrolment. The denominator is the number of enrolled participants in each study arm.

\*\* Participants are defined to have microbiologically confirmed TB if at least one confirmatory TB test (Ultra, AlereLAM) gives a positive result.

**Secondary endpoints** are:

Related to main objective

3.4.2.1 Time-to-TB-treatment-initiation among microbiologically confirmed cases and among all TB cases since enrolment. We will estimate Kaplan Meier curves and hazard ratios at day 7, 14, 28 and 56. Additionally we will compare the time to related estimates (median and IQR) of intervention and control group.

3.4.2.2 Proportion of cases re-admitted to hospital. The numerator will be the number of admissions for any reason (not included in the exclusion criteria) after initial discharge and within 8 weeks from enrolment. The denominator will be the number of participants enrolled.

---

3.4.2.3 Proportion of participants who are diagnosed with TB (irrespective of bacteriological confirmation) and have started on TB treatment within 72 hours of enrolment.

3.4.2.4 Proportion of participants who are diagnosed with microbiologically confirmed TB and are started on treatment at 7, 14 days and 8 weeks of enrolment.

3.4.2.5 Time to laboratory confirmed TB diagnosis and any TB diagnosis since enrolment.

3.4.2.6 Proportion of microbiologically confirmed TB participants started on treatment without Rif resistance information (only AlereLAM positive)).

Related to secondary objectives.

3.4.2.7 Eight-week all-cause mortality. The numerator will be the number of deaths during eight weeks after enrolment, the denominator the number of participants enrolled.

3.4.2.8 In hospital and 4-week all-cause mortality among all participants enrolled (assessed as the eight-week all-cause mortality).

3.4.2.9 Proportion of study participants who are able to provide the different specimens (sputum and urine samples) within 24, 48 and 72 hours of enrolment in the control and treatment arms.

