8.2 Secondary endpoints

- Eight-week all-cause mortality (main secondary endpoint) among all participants enrolled. The numerator will be number of deaths during eight weeks after enrolment, the denominator is the number of participants enrolled. We will compare this indicator between both study arms. In addition, this endpoint will also be calculated considering right censored observation when a participant is lost to follow up during the observation period or a

This project is part of the EDCTP2 programme supported by the European Union

participant experiences a different event that makes further follow up impossible.

- Time to TB treatment initiation among microbiologically confirmed cases and among all TB cases since enrolment. We will estimate Kaplan Meier curves (event= TB treatment initiation among laboratory confirmed TB patients and among all TB cases) and hazard ratios at day 7, 14, 28 and 56. Additionally we will compare the time to related estimates (mean and standard deviation) of intervention and control group.
- Proportion of cases re-admitted to hospital. The numerator will be the number of admissions after initial discharge and within 8 weeks from enrolment. The denominator will be the number of participants enrolled.
- The proportion of participants who are diagnosed with TB (irrespective of bacteriological confirmation) and started TB treatment within 72 hours of enrolment. The numerator is the number of participants diagnosed with TB (with or without bacteriological confirmation) who started treatment within 72 hours of enrolment; the denominator is the number of participants enrolled.
- The proportion of participants who are diagnosed with microbiologically confirmed TB and are started on treatment at 7 days, 14 days, 4 weeks and 8 weeks of enrolment. In addition, this endpoint will also be calculated considering right censored observation when a participant is lost to follow up or dead during the observation period or a participant experiences a different event that makes further follow up impossible.
- Proportion of participants who are able to provide sputum, stool and urine samples for Ultra/AlereLAM testing within 24, 48 and 72 hours of enrolment (the numerator is the number of urine samples or (and) sputum samples provided within 72 hours of admission and the denominator is the number of patients enrolled).

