### Exclusion criteria:

1. Unable to provide informed consent (if no authorized relatives are in the position to provide the consent).
2. Living outside the catchment area of the participating hospital(s).
3. With plans to migrate outside the catchment area within 2 months after recruitment.
4. Currently receiving anti-TB therapy or having received anti-TB therapy in the last 6 months prior to enrolment.
5. Receiving preventive TB treatment in the preceding 6 months
6. Participants admitted for traumatic reasons, acute abdomen, delivery or pregnancy (maternal conditions), or for planned/scheduled surgery.
7. Referred from other hospital
8. Positive result to a SARS-CoV-2 test (RT-PCR, antigen test, or other similar test that might define COVID-19 case in the study site)\*

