## 5 Sample Size

We expect the absolute difference in proportions of bacteriological confirmation between the two arms to be 7% (from 19% to 26% from the control to the intervention arm). Sample size was chosen to be sufficient to detect a 36.8% relative increase in the primary outcome in the intervention arm (as compared to the control arm).

Under this premise and the following assumptions:

- Alpha (two sided): 0.05
- Beta (power 80%): 0.2
- Estimated proportions of participants with microbiologically confirmed TB in the control arm 19% and in the intervention arm 26%
- Lost to follow up: 5% of recruited participants.

The study will recruit 586 PLHIV participants per trial arm, then we will include in the analysis 1172 participants in total. This number of participants will come from 4 sites (293 participants per arm at each site).

For this calculation we have used the following formulas based on Normal asymptotic approximation for proportions:

Sample Size formula

$$n_1 = \frac{\left( Z_{1-\alpha/2} \sqrt{(1 + \varphi) \bar{p}_1 (1 - \bar{p}_1)} + Z_{1-\beta} \sqrt{\varphi p_1 (1 - p_1) + p_1 (1 - p_1)} \right)^2}{\varphi |p_1 - \bar{p}_1|^2}$$

Power formula

$$\varphi = \frac{1 - w_1}{w_1}$$

$$\bar{p} = \frac{p_1 + \varphi p_2}{1 + \varphi}$$

$$1 - \beta = \Phi \left( \frac{|p_1 - \bar{p}| \sqrt{\varphi w_1} - Z_{1-\alpha/2} \sqrt{(1 + \varphi) \bar{p} (1 - \bar{p})}}{\sqrt{\varphi p_1 (1 - p_1) + p_2 (1 - p_2)}} \right)$$

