### 8.2 Secondary Efficacy Analyses

All secondary efficacy analyses will be calculated on ITT and Per protocol populations. The Secondary Efficacy Analyses are:

8.2.1 We will compare the proportion of deaths during eight weeks after enrolment between all participants enrolled in two study groups. We will test this differences using the test statistics  $z$  has an asymptotic standard normal distribution. These groups are microbiologically confirmed TB and therapy initiated within 72 hours from admission (numerator/success) and non-lab-confirmed TB or therapy not initiated within 72 hours (denominator/failure). We will compare, using Chi-square test or Fisher Test, these proportion values between intervention and control group.

8.2.2 We will estimate the Kaplan Meier curves to assess time to TB treatment initiation among those with microbiologically confirmed TB and among all TB (also including clinically diagnosed). We will compare both arms using the log rank test. We will use the KM procedure to calculate the survival rate from the survival function. If deemed necessary, to study the effects of some covariates and start of treatment over time we will use the Cox regression.

8.2.3 We will compare the proportion of cases re-admitted to hospital, to test this proportion we calculate the number of admissions after initial discharge and within 8 weeks from enrolment from all participants enrolled. We will compare, using Chi-square test or Fisher Test, these proportion values between intervention and control group.

8.2.4 We will compare the proportion of participants who are diagnosed with TB (irrespective of bacteriological confirmation and are started on TB treatment within 72 hours of enrolment). We will compare, using Chi-square test or Fisher Test, these proportion values between intervention and control group.

8.2.5 We will calculate the proportion of participants who are diagnosed with microbiologically confirmed TB and are started on TB treatment at 7d, 14d, 4 and 8 weeks of enrolment. We will compare, using Chi-square test or Fisher Test, these proportion values between intervention and control group.

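### The readmission endpoint has two conflicting numerators, and a death before discharge counts as not readmitted

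*SAP*

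**What the plan says.** Readmission to hospital is a secondary endpoint, and its numerator is written in two ways.

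- **With a filter on reason.** SAP 3.4 (item 3.4.2.2) takes the "number of admissions for any reason (not included in the exclusion criteria) after initial discharge and within 8 weeks from enrolment".
- **Without a filter.** The SAP's own analysis section, item 8.2.3, says "we calculate the number of admissions after initial discharge and within 8 weeks from enrolment from all participants enrolled". Protocol 8.2 agrees with that: "The numerator will be the number of admissions after initial discharge and within 8 weeks from enrolment". The protocol synopsis has the same definition.

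The filter does not say which exclusion criteria it means. The list in SAP 4.2 includes criterion 6, "Participants admitted for traumatic reasons, acute abdomen, delivery or pregnancy (maternal conditions), or for planned/scheduled surgery", and also criterion 4, "Currently receiving anti-TB therapy or having received anti-TB therapy in the last 6 months prior to enrolment".

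The denominator is the same everywhere. In SAP 3.4 it reads "The denominator will be the number of participants enrolled". No rule says how a death before discharge is handled for this endpoint. For treatment start at later time points, by contrast, protocol 8.2 adds an analysis that treats as a "right censored observation when a participant is lost to follow up or dead during the observation period".

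**The concern.** Two analysts following different sections of the same SAP would count different readmissions, and neither document says which section prevails. The trial is unblinded (protocol 10.6, SAP 4.3), so the choice should not be left until arm-level data can be seen.

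The scope of the filter also matters. If it were applied to the whole exclusion list, it could reach people who are on TB therapy when they are readmitted. Starting more people on TB therapy is what the intervention is meant to do, so the endpoint would then depend on a consequence of randomisation.

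The death issue is separate and applies to both numerators. A participant who dies in hospital during the first admission stays in the denominator and can never enter the numerator, and so receives the favourable score. The plan expects the intervention to lower mortality (protocol section 6, SAP 2.1). If it does, the intervention arm has more people left who can be readmitted.

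**Working it through.** The plan gives no expected readmission risk, so there is no figure of its own to reproduce here. The 586 per arm in SAP section 5 is used below only to turn percentages into counts.

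**1. Do the numerators differ even on the narrowest reading?** Take a participant who is discharged and then admitted after an injury in week 5. SAP 8.2.3 and protocol 8.2 count this admission. SAP 3.4.2.2 does not, because trauma is in criterion 6. The conflict therefore does not depend on any wide reading of the filter.

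**2. What does the filter cover?** The parenthesis qualifies the word reason. In the SAP list, criterion 6 is the item worded as reasons for admission. Criterion 4 is a treatment status, criterion 7 is referral from another hospital, and criterion 8 is a test result. Criterion 4 is also an entry test whose look-back period is tied to enrolment. The natural reading is therefore criterion 6 alone. Because no number is given, someone who applies the whole list afresh at readmission could treat a participant then on TB therapy as meeting criterion 4. The variable list in SAP 4.4 does not settle this, since it names no variable for readmission, its date or its reason.

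**3. How does a death before discharge affect the comparison?** Let r be the readmission risk among those discharged alive, taken as equal in both arms. Let d be the risk of in-hospital death. Ignoring people still in hospital at week 8:

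- Reported proportion = r × (1 − d)
- Spurious difference, intervention minus control = r × (d_control − d_intervention)

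The documents state neither r nor d, so these are assumptions. With r = 15%, d_intervention = 15% and d_control = 20%:

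- Intervention: 0.15 × 0.85 = 12.75%, or 0.1275 × 586 ≈ 75 participants
- Control: 0.15 × 0.80 = 12.00%, or 0.12 × 586 ≈ 70 participants
- Difference: 0.15 × 0.05 = 0.75 points against the arm with fewer deaths

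| Assumed r | No gap in deaths | 5-point gap | 10-point gap |
|---|---|---|---|
| 10% | 0 | 0.50 | 1.00 |
| 15% | 0 | 0.75 | 1.50 |
| 20% | 0 | 1.00 | 2.00 |

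(Percentage points against the arm with fewer in-hospital deaths.)

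For scale, the standard error of the difference in the worked case is √[(0.1275 × 0.8725 + 0.12 × 0.88) / 586] ≈ 1.92 points. The 0.75-point shift is about 0.39 standard errors.

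**The case against.** The protocol leaves analysis detail to the SAP (protocol 13.2), so adding a reason filter there is not an error in itself. That is fair, but it does not resolve a conflict between two sections of the SAP.

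The all-enrolled denominator is stated consistently and keeps the randomised comparison intact. Deaths are not hidden either. Eight-week mortality is the main secondary endpoint in the protocol, in-hospital and 4-week mortality are also endpoints, and SAP Table 4 reports deaths at week 8 by arm. This stands, and it is why the denominator should stay. A reader might infer that the endpoint understates readmission risk by 15–20%. That would hold only if it claimed to estimate risk among those discharged alive, and nowhere does it claim that.

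A reader might also infer that the filter will remove readmissions of treated TB patients and so flatter the intervention. One can put a number on this. If the treated shares were 26% and 19% and true readmission risk were 15% in both arms, the counted proportions would be 0.15 × 0.74 = 11.10% and 0.15 × 0.81 = 12.15%, a gap of 1.05 points. The documents do not support that as a finding. It needs the less natural reading of the filter. It equates microbiological confirmation (the 26% and 19% of SAP section 5) with being on treatment, although clinically diagnosed patients are treated as well and no arm gap in total treatment is given. It also assumes a readmission risk that the plan does not state. What remains is that the wording leaves this reading open.

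**Conclusion.** The plan has two written numerators for readmission, and this holds without any assumption. The filter most likely means criterion 6, but its scope is unnumbered, so its reach to participants on TB therapy is a possibility to close off and not an established bias.

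That a death before discharge scores as not readmitted follows directly from the definition. Its effect on the arm comparison is zero if in-hospital mortality is equal. It is about 0.75 points under the assumed 15% against 20% in-hospital death with 15% readmission after live discharge, and 0.5 to 2.0 points over the wider range shown. These sizes are illustrative only.

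Severity is low. Readmission is a secondary endpoint for which the trial was not powered, and neither the primary result nor the mortality analysis is touched.

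**What to change.** Use one numerator in SAP 3.4.2.2 and 8.2.3. Either delete the parenthesis, which restores agreement with the protocol, or limit it to exclusion criterion 6 by number in both places. If the filter is kept, add the readmission reason to the variables in SAP 4.4. Fix the choice before arm-level data are reviewed.

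Keep all enrolled participants as the denominator. Beside readmission, report death or readmission by day 56 by arm as a supportive analysis, so that an in-hospital death is not read as a good outcome.

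The cost is a wording change and one table row, using death dates that SAP 4.4 already lists. Without the filter, a few unrelated readmissions will be counted and will dilute the comparison slightly.
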